### **12.1. Statistical Analysis Methods**

#### **12.1.1. Analysis of Primary Efficacy Endpoint**

The primary efficacy endpoint is the number of confirmed HAE attacks in the FAS and PP populations. The number of HAE attacks will be analyzed by treatment group using appropriate descriptive statistics for the weekly attack rate, change and percentage change from baseline in attack rate, proportion of subjects with no attacks, and number of attack-free days. Efficacy analyses will be conducted for HAE attacks reported over the entire dosing interval (Days 1 to 28 inclusive) and during the effective dosing period in which BCX7353 should be at steady-state conditions (Days 8 to 28, inclusive). Efficacy endpoints will be summarized and listed for each treatment group.

Between-treatment comparisons (active vs. placebo and between active dose groups) for the weekly attack rate will be performed using an analysis of variance model and an analysis of covariance (ANCOVA) model. The adjusted qualifying attack rate will be included as a covariate in the ANCOVA model. The LSM for each treatment arm and the relative difference and associated 95% confidence intervals in attack rate between placebo and each active arm will also be calculated. If the difference between the 350mg and placebo is statistically significant,

additional dose response assessments will be analyzed based on the Tukey, Ciminera, and Heyse trend test.

The between treatment comparisons for the proportion of subjects who are attack free will be compared using a Fisher's exact test. If data warrant, a general linear model (Logistic regression) will also be used to test the dose response.

There will be no adjustments for multiplicity or previous interim analyses, if conducted, and all statistical tests will be 2-sided with an alpha of 0.05.

### 12.1.2. Supportive Analyses

The distribution of the HAE attacks will be examined. Cumulative distribution function of the confirmed attack rate will be produced by treatment group. A supportive analysis will be performed using a Poisson-regression model based on the number of confirmed attacks. The model will include Treatment and weekly interval as fixed effects.

The difference between the on treatment attack rate and the adjusted qualifying attack rate will be derived and summarized in tabular and graphical formats. Scatter plots of the adjusted qualifying attack vs. the confirmed attack rate and change from the adjusted qualifying attack rate will be presented. The individual attack rate over time will be plotted.

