### **5.3.3. Study BCX7353-203**

Interim efficacy, safety, PK, PD, and PK/PD results are available for Parts 1 and 2 of this ongoing proof-of-concept Phase 2 study in subjects with HAE. As of the cut-off date of 19 May 2017, 51 subjects with HAE were randomized and had received up to 28 days of treatment with BCX7353 once daily; 18 subjects received BCX7353 350 mg, 6 subjects received BCX7353 250 mg, and 7 subjects received BCX7353 125 mg. In addition, 20 subjects with HAE had received placebo. Part 3 of the study is currently ongoing.

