### 5.3.3.3. Interim Efficacy Results

Interim results for the primary efficacy endpoint, number of confirmed HAE attacks, and the secondary efficacy endpoint of number of HAE attacks analyzed by anatomical location, are presented for Parts 1 and 2 as of the cut-off date of 19 May 2017.

Statistically significant and clinically meaningful reductions in the rate of attacks were observed in subjects treated with BCX7353 compared to placebo. Reductions in attack rates were observed at all doses tested, compared to placebo. In the Full Analysis Set (FAS) for the Entire Dosing Period (Days 1-28), the Least Squares Mean (LSM) attack rate for placebo was 0.898 per week,

and a reduction in the confirmed attack rate of 0.434 attacks/week (48.4%,  $p < 0.001$ ) was observed for all BCX7353 doses combined compared to placebo. Reductions in confirmed attack rates by treatment group were: 350-mg dose group  $n = 18$ , 0.384 attacks/week, 42.8% reduction compared to placebo ( $p = 0.007$ ); 250-mg dose group  $n = 6$ , 0.417 attacks/week, 46.4% reduction compared to placebo ( $p = 0.039$ ); and 125-mg dose group  $n = 7$ , 0.579 attacks/week, 64.5% reduction compared to placebo ( $p = 0.003$ ). Consistent results were observed in the Per Protocol (PP) population and during the Effective Dosing Period (Days 8-28), the duration at which study drug was at steady state.

A prespecified secondary endpoint analyzed the rate of confirmed attacks by anatomical location, specifically attacks that included abdominal symptoms versus attacks with only peripheral symptoms. This analysis identified a dose-ordered difference in attack rate by anatomical location. A differential response in attack rate reductions was observed for attacks with objective peripheral symptoms compared to attacks with abdominal symptoms, particularly at the two higher doses (250 mg and 350 mg).

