#### **13.2.4. Analysis of Efficacy Variables**

As discussed in Section 7.2.1, each subject-reported HAE attack must be confirmed by an independent adjudication panel prior to inclusion in any statistical analysis or summary of efficacy.

There are no formal hypotheses planned for the study. The primary efficacy endpoint is the number of confirmed HAE attacks in the FAS population. The number of HAE attacks will be analyzed by treatment group using appropriate descriptive statistics as follows: weekly attack rate, counts of attacks, proportion of subjects with no attacks, and number of attack-free days. The relative change in attack rate from placebo will also be calculated for each active arm. Efficacy analyses will be conducted for HAE attacks reported over the entire dosing interval (Days 1 to 28 inclusive) and during the dosing period in which BCX7353 should be at steady-state conditions (Days 8 to 28, inclusive).

Efficacy endpoints will be summarized and listed for each treatment group. Between-treatment comparisons (active vs placebo and between active dose groups) for continuous efficacy variables will be performed using an analysis of variance (ANOVA) and an analysis of covariance (ANCOVA) model. The between treatment comparisons for the proportion of subjects who are attack free will be compared using a Fisher's exact test. A general linear model will be used to test the dose response. Additional statistical models may be considered and details will be provided in the statistical analysis plan.

There will be no adjustments for multiplicity and all statistical tests will be 2-sided with an alpha of 0.05.

Secondary efficacy endpoints including attack severity, location, duration and symptoms of attacks, and number of attacks requiring attack medication will be summarized for each treatment group.

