## 5. SAMPLE SIZE CONSIDERATIONS

Given that the BCX7353 response rate is unknown, the sample size was kept flexible to cover a range of response options that would achieve 90% power with an alpha of 0.05. The study population is expected to have a mean baseline attack rate of 1 attack/week. The expected mean reduction in attack rate of 350 mg BCX7353 QD is at least 70%. The mean reduction in attack rate in the placebo group may be as high as 30%. Sample size sensitivity assessments provided in Tables 2 and 3 are based on various BCX7353 and placebo responses and variability.

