**Table 2: Power assessment based on sample size and on-study attack rate**

Placebo			BCX7353			Power
Mean	SD	n	Mean	SD	N	
0.7	0.45	12	0.3	0.3	12	68%
0.7	0.45	12	0.3	0.45	12	55%
0.7	0.45	18	0.3	0.3	18	86%
0.7	0.45	18	0.3	0.45	18	74%
0.8	0.45	12	0.3	0.3	12	86%
0.8	0.45	12	0.3	0.4	12	79%
0.8	0.45	12	0.3	0.5	12	69%
0.8	0.45	18	0.3	0.3	18	97%
0.8	0.45	18	0.3	0.4	18	93%
0.8	0.45	18	0.3	0.5	18	87%

Note: Calculations were based on a 2-sided test at significance level of 0.05 and rates and SD are expressed in units.

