## **7. HYPOTHESES AND TREATMENT COMPARISONS**

### **7.1. Hypotheses**

This study is designed to evaluate the efficacy of once-daily prophylactic BCX7353 at 4 dose levels, as measured by the number of attacks of HAE observed in patients with HAE.

An estimation approach will be used to evaluate the dose-response relationship for BCX7353 and the treatment difference vs. placebo.

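### The supportive Poisson regression makes no allowance for between-subject variation, so its standard errors are too small under six of the ten rows of the SAP's own planning table

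*SAP*

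**What the plan says.** SAP 12.1.2 states: "A supportive analysis will be performed using a Poisson-regression model based on the number of confirmed attacks", and then: "The model will include Treatment and weekly interval as fixed effects". Nothing in either document adds a dispersion parameter, a subject effect, a robust variance or a negative binomial alternative. SAP section 16 lists the model for the entire and the effective dosing periods (Tables 14.2.1.9 and 14.2.2.9) by title only. By contrast, the repeated kallikrein model in SAP 14.1 does carry a random subject effect.

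Two passages come close. SAP 12.1.2 opens by saying that the distribution of attacks will be looked at, and SAP 11.3 lets methods change if assumptions prove violated at or before the data review meeting. Neither names overdispersion or a fallback.

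On the model's role, SAP 7.1 says: "An estimation approach will be used to evaluate the dose-response relationship for BCX7353 and the treatment difference vs. placebo". Protocol 13.2.4 says: "There are no formal hypotheses planned for the study". SAP 12.1.1 sets 2-sided tests at 0.05. The 95% intervals it mentions belong to the ANOVA/ANCOVA comparison; no interval or rate ratio is specified for the Poisson model.

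**The concern.** Subjects with HAE differ in their underlying attack rates. A Poisson model without a subject-level allowance ignores that spread and treats one subject's weekly counts as independent given treatment and week. If the spread is real, the standard error of the treatment effect is too small, and so is any p-value or interval derived from it.

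What is at stake is limited. This is the only count model set against an ANCOVA of skewed rates, in a plan that stresses estimation. A falsely narrow result would look like firm support for the primary analysis, mainly for an arm with a low attack rate. No decision rule uses it.

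**Working it through.** **Inputs.** SAP Table 2 ("Power assessment based on sample size and on-study attack rate"): placebo mean 0.7 or 0.8, SD 0.45; active mean 0.3, SD 0.3, 0.4, 0.45 or 0.5; 12 or 18 per arm. Its note does not name the units. I take attacks per week, because SAP section 5 plans on a baseline of 1 per week. Exposure is 28 days, or 4 weeks. Arm sizes planned through Part 3: placebo 18 + 2 + 2 = 22; 350 mg 18; 250 mg and 125 mg 6 + 6 = 12 each; 62.5 mg 6.

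**Table 2 itself.** Two-sample t-test power (noncentral t) reproduces all ten stated values within 1 percentage point, so the means and SDs are being read as intended.

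**Dispersion of the 28-day count.** Variance/mean V = (4·SD)² / (4·mean) = 4·SD²/mean.

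- Placebo: 0.81/0.7 = 1.16; 0.81/0.8 = 1.01.
- Active at 0.3 per week: 0.36/0.3 = 1.20 (SD 0.3); 0.64/0.3 = 2.13 (0.4); 0.81/0.3 = 2.70 (0.45); 1.00/0.3 = 3.33 (0.5). Six of the ten rows exceed 2.

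**Week effects do not help.** With complete weeks, the fitted treatment effect and its standard error equal those from subject totals. A trial fit gave a standard error of 0.2611 both ways.

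**Miss rate, worked for the row 0.8 vs 0.3, active SD 0.4, 18 per arm.** Expected attacks are 18 × 3.2 = 57.6 and 18 × 1.2 = 21.6.

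- Poisson variance of the log rate ratio: 1/57.6 + 1/21.6 = 0.0637.
- True variance: 1.0125/57.6 + 2.133/21.6 = 0.1163.
- Ratio 1.83; standard-error ratio 1.35.
- Miss rate 2·[1 − Φ(1.96/1.35)] = 14.7%.

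Closed form, and simulation with gamma or lognormal subject effects:

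| Active SD | Closed form, Table 2 sizes | Gamma, Table 2 sizes | Gamma, 22 vs 18 |
|---|---|---|---|
| 0.3 | 6.7–7.2% | 6.0–6.8% | 6.4–6.8% |
| 0.4 | 14.7% | 13–14% | 14.2% |
| 0.45 | 19.0% | 17–18% | 18.5% |
| 0.5 | 23.3% | 21–22% | 22.7% |

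Lognormal effects give about 13–20% over SD 0.4–0.5. For the effective dosing period (3 weeks, same between-subject variance, 22 vs 18) the figures are 5.7–6.1% at SD 0.3 and 12/15/18% at 0.4/0.45/0.5.

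**Interim rates.** Protocol 5.3.3.3 reports "the Least Squares Mean (LSM) attack rate for placebo was 0.898 per week". Subtracting the stated reductions gives 0.898 − 0.384 = 0.514 (350 mg), 0.898 − 0.417 = 0.481 (250 mg) and 0.898 − 0.579 = 0.319 (125 mg). Protocol 5.3.3 gives 18, 6 and 7 active subjects, and "In addition, 20 subjects with HAE had received placebo". Back-solving SD = (difference/t) / √(1/20 + 1/n), with t on 51 − 5 = 46 df (four arms and one covariate assumed) from p = 0.007, 0.039 and 0.003, gives 0.419, 0.422 and 0.421. That is one pooled SD. Two ways of dividing it between arms, at 22 vs 18/12/12:

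- *Variance proportional to the mean.* Mean rate weighted by arm size is (20×0.898 + 18×0.514 + 6×0.481 + 7×0.319)/51 = 0.634, so V = 4×0.42²/0.634 = 1.11 in every arm (SDs 0.50/0.38/0.37/0.30 for placebo/350/250/125 mg). Misses are about 6% in every arm; about 11% if the pooled SD is 0.50.
- *SD 0.42 in every arm.* V is 0.79 for placebo (simulated as Poisson) and 1.37/1.47/2.21 for 350/250/125 mg. Misses are 8/9/15%; 13/14/22% if the SD is 0.50.

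The 0.50 is an assumption: it applies if the covariate explained 1 − (0.42/0.50)² = 29% of the variance, because the Poisson model has no covariate.

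**Type I error against placebo.** With both arms at the placebo planning values, about 5–7%.

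**The case against.** The analysis is labelled supportive, and the plan leaves room to react: the distribution will be inspected and methods may be changed. That stands as a reason for a low rating. It does not close the gap, because both provisions are discretionary and name no remedy. Results for Parts 1 and 2 are already unblinded, so a variance method chosen later would be informed by the data.

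It is also fair that Table 2 is a sensitivity grid for a t-test, not a forecast. Four of its ten rows show almost no problem, and the top of the 13–23% range depends on gamma subject effects and on arm sizes.

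Three stronger readings are tempting and not supported:

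- A reader might infer that the interim data show 8–15% misses, because three p-values all return an SD of 0.42. If, as the back-solve assumes, they come from one model with one pooled error term, they must agree, and they say nothing about any single arm. Giving 0.42 to every arm makes placebo underdispersed and puts the excess on the low-rate 125 mg arm. Variance rising with the mean is at least as natural for counts, and gives about 6% throughout.
- A reader might infer that an interval specified in the SAP is wrong. SAP 12.1.2 specifies none for this model. The criticism is of the standard error, which drives the p-values and any interval that is reported.
- A reader might infer inflated false positives against placebo. At the planning values there is little inflation.

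**Conclusion.** The concern holds and is minor. As written, the Poisson model sets variance equal to mean, and six of the ten planning rows contradict that for the active arm. A 95% interval from its standard errors would miss about 6–7% of the time at active SD 0.3 and about 13–23% at SD 0.4–0.5, for arms of 12 or more. At the interim rates the range is about 6% to 15% at the back-solved SD of 0.42, and about 11% to 22% if the unadjusted SD is 0.50. The documents report no arm-level SD that would narrow this.

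The figures assume weekly units in Table 2, complete 28-day exposure, no covariate, and gamma subject effects unless stated. The primary ANOVA/ANCOVA is unaffected.

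**What to change.** Keep the Poisson mean model and add one sentence to SAP 12.1.2: the variance will be a subject-level robust (sandwich) estimate, from a Poisson GEE clustered on subject or from one total count per subject with log exposure as offset, with a small-sample leverage (jackknife-type) correction and a t reference.

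For subject totals Yᵢ with arm sum T, each arm contributes [n/(n − 1)]² Σ(Yᵢ − Ȳ)²/T². With t on 70 − 5 = 65 df, misses fall to about 4.6–4.9% at SD 0.3 and 5.5–7.2% at SD 0.4–0.5 (up to 7.6% at 22 vs 12).

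The sentence should be this specific because nearby options do less:

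- A scale parameter estimated from weekly rows still misses 11.7–17.8% at SD 0.4–0.5. Within one week, V = 2.13 shows up as only about 1 + 1.13/4 = 1.28.
- A negative binomial model with one common dispersion leaves 11/12/16% at SD 0.4/0.45/0.5 (22 vs 18).
- With only an n/(n − 1) correction, the 6-subject 62.5 mg arm at SD 0.3 misses 7.1–7.4%, against 5.3% for plain Poisson and 4.5–4.6% with the leverage correction.

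The cost is a few lines of SAS and wider intervals: about 1.1 times at SD 0.3 and 1.3–1.6 times at SD 0.4–0.5. Coverage stays slightly short of 95% at SD 0.5, and is slightly conservative in the 6-subject arm (3.8–4.6% misses at 0.3 per week).

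### The supportive Poisson model leaves out the adjusted qualifying attack rate, so no baseline-adjusted count analysis stands beside the primary ANCOVA

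*SAP*

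**What the plan says.** - **Count model (SAP 12.1.2).** A Poisson regression on the number of confirmed attacks is planned as a supportive analysis: "The model will include Treatment and weekly interval as fixed effects". No scale parameter, robust variance or subject effect is stated.
- **Primary analysis (SAP 12.1.1).** Weekly attack rates are compared in two ways, "performed using an analysis of variance model and an analysis of covariance (ANCOVA) model", and "The adjusted qualifying attack rate will be included as a covariate in the ANCOVA model".
- **Other models.** The sensitivity ANCOVAs (12.1.3) keep a qualifying rate as covariate, and so does the ANCOVA for the Angioedema Activity Score (12.1.4).
- **General rule (SAP 9.3).** Gender, age and qualifying attack rate are to be covariates in the primary efficacy assessments, if data permit.
- **Baseline information.** SAP 10.3 derives the adjusted qualifying rate for each subject. SAP 5 says the population is "expected to have a mean baseline attack rate of 1 attack/week". It gives no SD for that rate and no correlation with the on-study rate.
- **Randomisation (Protocol 9.3.2).** The schedule is computer-generated, and no stratification factor is named.

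**The concern.** Eligibility needs at least 2 attacks per month over 93 days, that is 6 attacks or 6 x 7/93 = 0.45 per week, with no upper limit. Baseline rates may therefore vary widely around the expected mean of 1 per week. The plan itself treats the qualifying rate as informative: it adjusts for it in the ANCOVAs and uses it to impute missing diary days in the baseline-carried-forward analysis.

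The Poisson model is the planned count-based check on a normal-theory analysis of small-sample attack rates. Without the covariate, its rate ratios carry whatever baseline imbalance the small arms happen to have. If it then disagrees with the ANCOVA, the table alone will not show whether the distribution or the baseline adjustment is responsible.

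**Working it through.** **1. The plan's own power figure.** SAP Table 2, placebo 0.7 vs active 0.3, SD 0.45, 18 per arm: noncentrality = 0.4/(0.45 x sqrt(2/18)) = 0.4/0.15 = 2.67 on 34 df. Power is 73.6%, against 74% stated. All ten cells reproduce within 1 point as unadjusted two-sample t-tests, so the sizing says nothing about the covariate's value.

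**2. Arm sizes under the three-part SAP.** Part 1 (36, 1:1) gives 18 placebo and 18 at 350 mg. Part 2 (14, 1:3:3) gives 2, 6, 6. Part 3 (20, 1:3:3:3) gives 2, 6, 6, 6. Pooled: placebo 22, 350 mg 18, 250 mg 12, 125 mg 12, 62.5 mg 6. Of the 22 placebo subjects, 18 come from Part 1. The 125 and 250 mg arms have only 4 concurrent placebo subjects and the 62.5 mg arm has 2.

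**3. Chance imbalance.** SD of the difference in mean qualifying rate, in baseline SDs = sqrt(1/22 + 1/n). The last column assumes a baseline CV of 25 to 50%, which the documents do not give.

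| n active | 1 SD | 95% range | as % of mean rate |
|---|---|---|---|
| 6 | 0.46 | ±0.90 | 12 to 23% |
| 12 | 0.36 | ±0.70 | 9 to 18% |
| 18 | 0.32 | ±0.62 | 8 to 16% |

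This is chance only. Any shift in population between parts would be additional; the documents show none.

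**4. How much reaches the rate ratio.** Simulated trials: 22 placebo, qualifying count over 93 days with at least 6 attacks, 28-day on-study counts, equal true rates in both arms. The correlation between baseline imbalance and the unadjusted log rate ratio is about 0 if the qualifying rate does not predict on-study attacks. It is about 0.3 if prediction is weak (on-study rate follows the square root of the baseline rate) and 0.55 to 0.7 if it is proportional.

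**5. Effect of adding the covariate.** Quasi-Poisson model (scale parameter estimated), assumed true rates 0.8 vs 0.4 per week. Read across, not down: on-study variation unrelated to baseline differs between scenarios.

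| Prediction | CV | n | SD of log RR, without → with | variance ratio | power, without → with |
|---|---|---|---|---|---|
| none | 0.5 | 12 | 0.328 → 0.332 | 1.03 | 62.2 → 60.5% |
| none | 0.5 | 18 | 0.270 → 0.272 | 1.02 | 76.0 → 74.0% |
| weak | 0.5 | 12 | 0.288 → 0.283 | 0.96 | 65.2 → 68.2% |
| weak | 0.5 | 18 | 0.247 → 0.244 | 0.97 | 82.3 → 83.0% |
| proportional | 0.5 | 12 | 0.317 → 0.285 | 0.81 | 64.2 → 78.0% |
| proportional | 0.5 | 18 | 0.258 → 0.230 | 0.80 | 78.0 → 87.3% |
| proportional | 0.7 | 12 | 0.383 → 0.320 | 0.70 | 50.7 → 63.2% |
| proportional | 0.7 | 18 | 0.320 → 0.266 | 0.69 | 58.3 → 76.7% |

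Over n = 6, 12 and 18 the variance ratio is about 1.02 to 1.03 (none), 0.96 to 0.99 (weak) and 0.69 to 0.83 (proportional).

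**6. The reported standard error.** In an unscaled Poisson model, fitted totals per arm equal observed totals. The model-based variance of the log rate ratio is therefore 1/Y(active) + 1/Y(placebo) without the covariate, and cannot be smaller with it. In 600 simulated trials at each of CV 25, 40 and 50% (12 vs 22, four weekly counts), the adjusted/unadjusted SE averaged 1.013 to 1.014 and was never below 1. The gains in step 5 are in the estimator's actual variability; a reported interval reflects them only with a scale or robust variance.

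**7. Where in the range.** If counts over 4 weeks are Poisson within subject, the variance of a weekly rate is mean/4. For placebo in Table 2 (SD² = 0.2025), 0.7/4 = 0.175 leaves 0.0275 between subjects (CV sqrt(0.0275)/0.7 = 24%), and 0.8/4 = 0.200 leaves 0.0025 (CV 6%). The active arm allows more: 0.3/4 = 0.075 of 0.09 to 0.25 leaves 17 to 70% of the variance between subjects. The planned placebo SDs thus point to the low end of the gain.

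**The case against.** **The unadjusted ANOVA.** SAP 12.1.1 runs an ANOVA beside the ANCOVA. ANOVA against Poisson isolates the distributional assumption, and ANOVA against ANCOVA shows the baseline effect. This stands: a reader might infer that the Poisson model has no like-for-like partner, but the ANOVA is one. What remains missing is an adjusted count model to set beside the ANCOVA.

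**SAP 9.3 may already cover it.** It speaks of primary efficacy assessments, if data permit. The Poisson model is labelled supportive and names its own terms, so 9.3 does not clearly add one.

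**The gain is unproven.** This largely stands. Proportional prediction is an assumption, and the placebo SDs suggest a modest benefit. A reader might also infer that the planned intervals are wider than the data allow; for an unscaled Poisson model that is wrong (step 6).

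**The attack-free analysis.** A reader might extend the point to it: "The between treatment comparisons for the proportion of subjects who are attack free will be compared using a Fisher's exact test". The documents do not support that. Fisher's test takes no covariate and is a sound unadjusted test. The logistic dose-response model is conditional, its terms are not stated, and the attack-free proportion sits under the primary endpoint, where 9.3 may apply. In simulation, adjusting a like-for-like score test moved power by only about -1 to +4 points.

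**It is only a supportive model.** Protocol 13.2.4 plans no formal hypotheses, and the primary ANCOVA is already adjusted. This limits the weight of the point but gives no reason to omit the term.

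**Conclusion.** The point holds as a cheap improvement to a supportive analysis. The omission is explicit, and chance imbalance of 0.32 to 0.46 baseline SDs (1 SD) can enter the unadjusted rate ratio, most of all at 62.5 mg. Its effect depends on two quantities the documents do not give: the SD of the qualifying rate and its correlation with the on-study rate. Across the assumed scenarios, the variance of the log rate ratio rises by 2 to 3% at worst and falls by 17 to 31% at best.

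It would be too strong to infer that the unadjusted Poisson comparison is biased or has an inflated type I error because the covariate is missing. Randomisation keeps unadjusted comparisons free of systematic baseline bias on average. Pooling mostly Part 1 placebo with the lower doses weakens that protection, but no difference between parts is shown. The model's unstated handling of overdispersion is a separate matter, and it decides whether any gain appears in the reported intervals.

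**What to change.** In SAP 12.1.2, add log(adjusted qualifying attack rate) as a covariate to the Poisson model, for Tables 14.2.1.9 and 14.2.2.9. State whether its standard errors use a scale parameter or a robust variance, since the reported intervals cannot otherwise narrow. Leave Fisher's exact test as it is.

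The cost is one term and one degree of freedom. The covariate is already derived under SAP 10.3. Its logarithm is defined for every eligible subject, because merging attacks on consecutive days still leaves at least one attack. If the qualifying rate proves uninformative, the expected loss is about 2 to 3% in variance.
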